### 4.2 Patient disposition

A patient disposition table will include the number of patients screened, patients in the safety, PP analysis sets, completers and withdrawals with reason for withdrawal, and finally patients by visit will be summarised with frequency and percentage.

The patients screened but not allocated to treatment will be presented with the reason(s) for screening failure in a listing

All major protocol deviations will be summarised with frequency and percentage for each category of protocol deviation.

### 4.3 Demographics and other baseline characteristics

The following demographic and body measurements variables will be summarised: age, sex, race, height, weight and BMI.

Medical and surgical history and concomitant illness will be summarised by MedDRA system organ class (SOC) and preferred term (PT) version 18.1. Prior and concomitant medication will be tabulated by WHO drug version 153E, level 4 (chemical/therapeutic/pharmacological subgroup) and level 5 (Chemical substance). Medication is categorised as “Started prior to study start” and “Ongoing” in the eCRF and these responses will be used to categorise as prior and concomitant respectively. Medication was recorded in the original eCRF. The additional data recording collected specifically medication for de-sensitization and rejection. There may therefore be an overlap with prior and concomitant medication and the de-sensitization and rejection medication will be tabulated separately.

Previous kidney transplant history will be summary tabulated.

Baseline assessments of ECG, physical examination, vital signs, body measurements and laboratory parameters will be presented as part of the general tables and listings for these parameters.

ImmunoCAP IgE (ADA) is recorded at baseline only and will be listed. Serology and sperm sample will be listed.

The drug exposure will be listed showing number of doses, planned dose and actual dose per kg BW.

Donor characteristics will be listed.

Recipient and donor HLA types will be listed.

Recipient and donor blood groups will be listed.

Deceased donor characteristics will be listed.

Protocol deviations will be listed.

## **4.4 Efficacy**

### **4.4.1 Primary efficacy analysis**

The primary efficacy endpoint is defined as imlifidase ability to create a negative crossmatch test within 24 hours after imlifidase dosing. The primary endpoint will be presented for the PP analysis sets.

The planned time points (according to the flowchart) are: Screening, pre-dose, 2h, 6h, 24h, and 48h. In general, only the pre-dose and 24h analyses are performed, while the other planned analyses are missing. For each of the crossmatch tests (FACS B-cell, FACS T-cell, amplified and non-amplified analyses of CDC B-cells and CDC T-cells, and virtual) summary tabulations by time point will be made.

For each patient an overall response is defined as positive if at least one of the assays is positive at pre-dose and all recorded assays are negative at 24h. The overall response is summary tabulated.

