### **3 Analysis sets**

The analysis sets will be determined at the data review prior to database lock. Decisions will be documented in the database lock minutes.

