#### **3.2 Per protocol analysis set**

The Per protocol analysis set (PP) will consist of all patients in the safety set that has recorded at least one efficacy endpoint value. Data from patients with one or more major protocol violations are excluded. The PP analysis set will be used for presentation of efficacy, pharmacokinetic, and pharmacodynamic endpoints.

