## 4 Statistical analyses and presentation of data

### 4.1 General considerations

No formal statistical hypothesis testing will be performed in this study. All presentation of data will be descriptive by nature. Missing data will in general not be imputed or adjusted for in other ways.

The protocol states that tabulations will be by actual dose received. The protocol allowed for the DSMB to decide on dose escalation. All patients were administered planned dose(s) of 0.25 mg/kg BW. For one patient the actual dose was reduced due to an allergic reaction. For 3 patients the protocol option of administering a 2nd dose was used. Efficacy and safety tabulations will be by number of administrations (1 or 2 doses) and total including all patients. The patient with reduced dose [REDACTED] will be included in the “1 dose” group for safety evaluation but excluded from the PP.

Numerical data will be presented in summary tables by number of patients, arithmetic mean (geometric mean and coefficient of variation [CV] where applicable), median, standard deviation (SD), minimum and maximum. Categorical data will be presented by number and percent of patients as well as number of events (where applicable).

Endpoints will be presented graphically as mean profile plots, individual profile plots and spaghetti plots. The sampling frequency is for efficacy and some safety endpoints high from pre-dose until 48 hours followed by decreasing frequency. Therefore, the graphical presentation will, in most cases, be as box plots with a categorical x-axis. For other data, a plot with linear x-axis (0 to 180 days) may be supplemented with a subset plot where only the first 24 or 48 hours are included on the x-axis.

All data will be listed. Auxiliary database parameters will not be included. Listings will be sorted by patient ID, parameter and time point. In general listings will not be mentioned in detail below.

The study did not include any interim analyses.

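### The primary endpoint is reported only for the per-protocol set, which leaves out a treated patient whose dose was reduced for an allergic reaction

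*SAP*

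**What the plan says.** The SAP defines two sets. The safety set holds everyone who received study drug. PP (3.2) holds safety-set patients with at least one efficacy value, subject to one exclusion: "Data from patients with one or more major protocol violations are excluded". On its use, 3.2 says: "The PP analysis set will be used for presentation of efficacy, pharmacokinetic, and pharmacodynamic endpoints". Section 4.4.1 repeats this for the primary endpoint ("The primary endpoint will be presented for the PP analysis sets"), and 4.4.2 does so for the secondary efficacy endpoints.

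Section 4.1 reports what happened to one patient: "For one patient the actual dose was reduced due to an allergic reaction". That patient is put in the one-dose "group for safety evaluation but excluded from the PP". The same section says of the columns: "Efficacy and safety tabulations will be by number of administrations (1 or 2 doses) and total including all patients". Section 3 leaves the final set decisions to the data review before lock: "Decisions will be documented in the database lock minutes".

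Protocol 12.1 defined three sets: safety, a FAS (treated patients with an anti-HLA measurement in the first 24 hours) and a per-protocol set whose criteria were to be settled once all deviations were known. It did not say which set served the primary endpoint. The SAP does not mention the FAS. SAP Section 5, which lists departures from the protocol analysis, contains one item: who performs the pharmacokinetic analysis.

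**The concern.** The proportion of patients whose crossmatch turns negative is the main result here. There is no control arm and no hypothesis test, so that proportion and its denominator are what a reader takes away. Taking a treated patient out of the denominator because of an allergic reaction ties the exclusion to the treatment itself. On the natural reading the reaction came during or after dosing, so this is not a baseline eligibility matter. If a patient with a reduced dose was less likely to convert, the PP rate is too high.

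Three gaps in the text make this harder to judge:

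- **Ground for exclusion.** Section 4.1 gives the fact (a reduced dose) but does not say whether it counts as a major protocol violation or whether the patient has no efficacy value. Those are the only two routes out of PP in 3.2.
- **Meaning of the total.** The total promised in 4.1 names no analysis set.
- **The FAS.** The protocol's broader set was dropped, and the section meant for such changes does not record it.

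**Working it through.** **Reading the total column.** Section 4.1 can be read in two ways.

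- If the total means all treated patients, also for efficacy, it contradicts 3.2 and 4.4.1, which confine efficacy to PP.
- If it means both dose groups within PP, it agrees with them, but no efficacy summary over all treated patients is then planned.

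**Inputs for the size.** The plan gives no figure to reproduce.

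- Number treated, N = 15–20. This is the planned range (SAP 2.2); the final number is not given, so it is an assumption.
- Two-dose patients: 3. SAP 4.1 says "For 3 patients the protocol option of administering a" second dose was used.
- Patients in PP = N − 1. Assumption: the reduced-dose patient is the only exclusion.
- Other non-responders, k = 0–2. Assumption.
- This patient's crossmatch result: not in the documents, so each case is shown.

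**Total column, patient did not convert.** Difference = (N − 1 − k)/(N − 1) − (N − 1 − k)/N.

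- N = 15, k = 0: 14/14 − 14/15 = 100% − 93.3% = +6.7 points.
- N = 20, k = 2: 17/19 − 17/20 = 89.5% − 85.0% = +4.5 points.

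**Total column, patient converted.** Difference = (N − 1 − k)/(N − 1) − (N − k)/N.

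- k = 0: both rates are 100%, difference 0.
- N = 15, k = 2: 12/14 − 13/15 = 85.7% − 86.7% = −1.0 point.

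**One-dose column.** Treated M = N − 3 = 12–17; in PP, M − 1 = 11–16. The k other non-responders are all assumed to be in this column. The formulas are the same with M in place of N.

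- Did not convert, M = 12, k = 0: 11/11 − 11/12 = 100% − 91.7% = +8.3 points.
- Did not convert, M = 17, k = 2: 14/16 − 14/17 = 87.5% − 82.35% = +5.1 points.
- Converted, k = 0: difference 0.
- Converted, M = 12, k = 2: 9/11 − 10/12 = 81.8% − 83.3% = −1.5 points.

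**Patient not evaluable.** With no positive pre-dose assay or no 24-hour result, the rate among evaluable patients equals the PP rate. The difference is 0, and only the separate count changes.

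**Precision.** Exact (Clopper-Pearson) 95% intervals: 14/14 gives 76.8–100% and 14/15 gives 68.1–99.8%; 19/19 gives 82.4–100% and 19/20 gives 75.1–99.9%. If this patient is the only non-responder, the lower limit falls by about 7 to 9 points when the patient is included.

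**The case against.** The strongest reply is that nothing is hidden. Section 4.1 identifies the patient and gives the reason. A dose below the planned one points to the major-violation criterion, and the formal classification may be in the lock minutes or the deviation tables. Part of the sentence is redacted, which cannot be held against the plan. Set sizes and major deviations are tabulated (4.2), and actual dose (4.3) and crossmatch results (4.4.2) are listed, so a reader could rebuild the all-treated rate. All of this stands. The data are there; what is missing is the planned summary and the stated criterion.

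On the FAS, the protocol never assigned it to the primary endpoint, it depends on an anti-HLA measurement and not on crossmatch, and this patient's membership is unknown. That also stands. No prespecified primary set was switched; a defined set was removed without being declared.

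The total can reasonably be read as within PP. That removes the contradiction but confirms that no all-treated efficacy summary is planned.

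It can also be said that pooling a reduced dose with full doses in the one-dose column sits badly with protocol 12.2.1, which presents data by actual dose received. This is a fair reason to mark the patient by actual dose, but not to leave the patient out of every efficacy table.

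Finally, the size rests on assumptions and the range includes zero. That is correct, and it limits the claim to possible bias.

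**Conclusion.** The concern holds and should be fixed. Followed as written, the SAP gives a primary response rate that omits a treated patient because of a tolerability event. It does not state the 3.2 criterion, plans no unambiguous all-treated summary, and does not declare that the FAS was dropped.

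Under the assumptions above, one patient moves the total rate by up to 6.7 points and the one-dose rate by up to 8.3 points if that patient did not convert. If the patient converted, the PP rate is at most 1.0 and 1.5 points too low, respectively. Confidence is high on the gaps in the text; the direction and size of any bias depend on a result the documents do not give. No test or decision rule is affected.

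**What to change.** Keep PP and add the following:

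- **4.4.1:** Beside PP, tabulate the overall response for all treated patients (the safety set), using the section's existing rule and no imputation. Include the reduced-dose patient with the recorded result, marked by actual dose received. Show patients without a positive pre-dose assay and patients without a 24-hour result as two separate counts, so that nobody is reclassified as a non-responder.
- **4.1:** Say which set the total refers to for efficacy. Name the 3.2 criterion that removes this patient from PP, or refer to the lock minutes.
- **Section 5:** Declare that the protocol's FAS was removed and that PP became the only efficacy set.

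Exact confidence intervals are optional. The cost is one table column with two count lines, from data already collected and listed, and a few sentences. The only downside is that a slightly lower rate may appear beside the PP rate.

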Patients found eligible at the screening visit will be included in the study. At visit 2 the eligibility check will be repeated within 60 min from IdeS dosing. A pregnancy test will be taken. If a female patient has been hospitalized between screening visit and visit 2, a pregnancy test at screening visit will suffice and a pregnancy test at visit 2 is not required. In addition methylprednisolone and loratadine will be administered predose to prevent infusion reactions. Vital signs, body temperature, safety laboratory sampling, pharmacokinetic and pharmacodynamics sampling will be performed pre-dose, 2 h, 6 h, 24 h and 48 h post IdeS infusion. In addition blood sampling for DSAs will be drawn at pre-dose, 2 h, 6 h, 24 and 48 h. Blood sampling for CDC- and FACS-CXM will be done at pre-dose, 2 h, 6 h, and 24 h. Any effort should be made to obtain crossmatch test for all time-points indicated in the study flowcharts. If this is not possible due to logistics on specific sites, the sponsor can allow a smaller number of time-points to be evaluated. However, as a minimum one crossmatch test pre-dose and one post-dose IdeS must be performed to allow evaluation of the primary endpoint. ADA will be sampled at pre-dose and 48 h post IdeS infusion. P-creatinine will be measured at 24 h and 48 h post IdeS infusion and eGFR will be calculated. Repeat 24 hour urine collections will be performed day 1-9 for urine protein electrophoresis analysis. AEs and concomitant medication will be recorded in the CRF throughout the visit. AEs that occur in the time period prior to administration of the study drug should be recorded as part of the patient's medical history but will not be considered a treatment emergent adverse event (TEAE) unless directly related to study procedures (e.g. hematoma secondary to laboratory testing) or it meets the definition of an SAE. A kidney biopsy on the donor kidney will be performed in deceased donor patients.

Visit 3 (day 3-6)

Twenty-four- (24)-hour urine collections will be performed daily, day 1-9, for urine protein electrophoresis analysis. AE and concomitant medication will be assessed. PK will be drawn at 96 hours \pm 4h.

Visit 4 (day 7)

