#### 1.1.2 Endpoints

**The primary endpoint of this study is:**

- Efficacy defined as imlifidase ability to create a negative crossmatch test within 24 hours after imlifidase dosing

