## **Time to negative crossmatch**

The time to creating a negative crossmatch is specified in the protocol as an endpoint. However, due to many missing values and in particular missing data for time points between pre-dose and 24 hours, the Time to creating a negative cross match will not be calculated. Crossmatch data will be listed.

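### The primary response rule does not require the assay that was positive pre-dose to be retested at 24h, so an untested conversion can count as a response

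*SAP*

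**What the plan says.** SAP 1.1.2 gives the primary endpoint as "Efficacy defined as imlifidase ability to create a negative crossmatch test within 24 hours after imlifidase dosing". SAP 4.4.1 turns this into an overall response per patient, "positive if at least one of the assays is positive at pre-dose and all recorded assays are negative at 24h", tabulated for the per-protocol (PP) set. Seven assays feed it: FACS B-cell, FACS T-cell, CDC B-cell and CDC T-cell (each amplified and non-amplified), and virtual. Each assay also gets its own summary by time point.

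On the data available, SAP 4.4.1 states: "In general, only the pre-dose and 24h analyses are performed, while the other planned analyses are missing". SAP 4.4.2 drops the time-to-negative-crossmatch calculation "due to many missing values and in particular missing data for time points between pre-dose and 24 hours".

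On what must be measured, Table 2 in both documents schedules CDC and FACS crossmatches together at pre-dose, 2h, 6h and 24h. It lists no virtual crossmatch. Protocol 6.2 (Visit 2) lets the sponsor accept fewer time points for site logistics, but "as a minimum one crossmatch test pre-dose and one post-dose IdeS must be performed to allow evaluation of the primary endpoint".

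On who is analysed and how gaps are handled, the PP set in SAP 3.2 is "all patients in the safety set that has recorded at least one efficacy endpoint value", less patients with major protocol violations. SAP 4.1 adds: "Missing data will in general not be imputed or adjusted for in other ways".

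**The concern.** Protocol 2.5 presents the endpoint as conversion of the crossmatch, with patients serving as their own controls. In a single-arm study that within-patient comparison is the only control, so the flag should rest on the same test before and after dosing.

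The rule does not ensure this. Its first condition is met by any positive assay at pre-dose. Its second looks only at whatever was recorded at 24h. Take a patient who is FACS B-cell positive at pre-dose and whose only 24h record is a negative CDC T-cell result. Both conditions are met and the patient is a responder, although the positive assay was never repeated.

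The flag is the trial's primary result, and its summary row would not show how many responses were of this kind. A reader would have to rebuild it patient by patient from the listings.

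A lesser gap sits beside this one: the rule gives no score to a patient with no 24h result at all.

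**Working it through.** The plan states no target rate, power or calculated sample size, so there is no figure of its own to reproduce. The check has four steps.

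**1. Does other text supply the missing link?** No.
- The minimum in Protocol 6.2 is one test before and one after dosing. It names neither the same assay nor the 24h time point.
- PP entry needs one efficacy value of any kind, so it does not require a 24h crossmatch.
- The no-imputation sentence in SAP 4.1 does not say how the flag is derived.
- SAP 3 has the analysis sets settled before database lock. That decides who is counted, not how they are scored.

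**2. Direction.** Hold the set of assays fixed, use pre-dose as baseline, and require at least one 24h result. A matched rule keeps both SAP conditions and adds a third: each pre-dose-positive assay must itself have a negative result. Adding a condition can only remove responders. With two assays A and B, the SAP rule gives 3 × 3 = 9 response patterns:

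| Pre-dose positive | 24h: A and B negative | 24h: only A recorded, negative | 24h: only B recorded, negative |
|---|---|---|---|
| A and B | matched | B not retested | A not retested |
| A only | matched | matched | A not retested |
| B only | matched | B not retested | matched |

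Five patterns are matched, four are not, and none goes the other way. These are counts of patterns, not probabilities.

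**3. Size.** SAP 2 plans 15 to 20 patients. SAP 4.1 excludes one reduced-dose patient from PP. With no further exclusions, PP N is 15 − 1 = 14 to 20 − 1 = 19. For k affected patients the shift is 100k/N points:
- k = 1: 100/14 = 7.1; 100/19 = 5.3
- k = 2: 200/14 = 14.3; 200/19 = 10.5

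As an illustration, suppose every PP patient responds under the current rule and one conversion was untested. Then 100% becomes 13/14 = 92.9% or 18/19 = 94.7%. Further exclusions would enlarge the shifts.

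**4. Does the direction survive a change of baseline?** No. Table 1 also schedules a screening crossmatch. Suppose the baseline becomes the last result before dosing, so that screening fills in where pre-dose is missing. A patient positive at screening, with no pre-dose result and negative at 24h, then moves from non-response to response.

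For two assays, let each screening and pre-dose result be positive, negative or missing, with at least one 24h result. SAP responses number 5 × 3 × 9 = 135 (pre-dose patterns with a positive × qualifying 24h patterns × screening patterns). Of these, 75 are also responses under the changed rule and 60 are not. A further 21 patterns respond only under the changed rule: 6 + 6 where one assay lacks a pre-dose result, and 9 where both do. The one-way direction therefore depends on keeping pre-dose as baseline.

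**The case against.** The strongest reply is that the schedule makes the case unlikely. Table 2 pairs CDC and FACS at pre-dose and at 24h, and Protocol 6.2 relaxes time points, not assays. A FACS result before dosing with only CDC at 24h would depart from the schedule in a way that no section permits or reports. SAP 4.4.1 also says that the pre-dose and 24h tests are the ones generally performed. The analysis is descriptive, all data are listed, and with at most 19 PP patients the per-assay tables would show gaps. This stands as a limit on likely impact. It does not repair the flag, which would still score such a patient as a responder.

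Two further points stand and shape the fix. A matched rule applied to all seven assays would fail a patient for an unrepeated virtual crossmatch that Table 2 never schedules. And, as step 4 shows, bringing in screening results can raise the rate.

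Some stronger readings are tempting but unsupported:
- A reader might infer that the reported rate is inflated. No document shows an affected patient.
- A reader might take the many missing values in SAP 4.4.2 to mean missing 24h results. That sentence points in particular to the times between pre-dose and 24h.
- A reader might say that a patient with no 24h result counts as a responder, since zero records contain no positive. The ordinary reading, in line with SAP 4.1, is that such a patient is missing. A patient with no post-dose crossmatch would also breach the Protocol 6.2 minimum and might leave PP, although SAP 3.2 does not define a major violation.

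**Conclusion.** The concern holds as a fault in the stated rule: as written, it can count an unobserved conversion as a response on the primary endpoint. With pre-dose as baseline, a fixed set of assays and at least one 24h result, the error runs only towards a higher rate, by 5.3 to 7.1 points per affected patient. That range assumes the planned 15 to 20 patients and a single PP exclusion. The number affected is not stated and may be zero, so this is a rule to correct before the result is read, not evidence that the result is wrong. The missing score for a patient with no 24h result is a lesser point, settled by the same wording.

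**What to change.** Keep the SAP's pre-dose baseline and define response by three conditions:
1. At least one CDC or FACS assay is positive at pre-dose.
2. Every CDC or FACS assay positive at pre-dose has a recorded negative result at 24h. If its 24h result is missing, its latest recorded result within 24 hours of dosing must be negative.
3. No recorded CDC or FACS assay is positive at 24h.

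Score a pre-dose-positive CDC or FACS assay with no post-dose result within 24 hours as *conversion not shown*. Keep that patient in the PP denominator as not having responded, and report the number of such patients. State that this is a scoring convention beside the general no-imputation sentence in SAP 4.1.

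Add three labelled rows:
- The result with the virtual crossmatch included. In the main row, an unrepeated virtual test alone should not cause non-response. Leaving the virtual test out can move individual patients either way. For example, a patient whose only positive at 24h is virtual would become a responder. The separate row shows this.
- If screening results are used where pre-dose is missing, a sensitivity row that says so, because it can raise the rate.
- The current SAP rule, adjacent to the main row.

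List the change in SAP Section 5, which now records only who performs the PK analysis.

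The cost is a few sentences of SAP text and re-derived flags from data already collected. There are two downsides. The scoring is conservative for unrepeated assays. The change is also data-informed, as the SAP itself was, since it already describes the pattern of missing crossmatches. Showing the current rule alongside keeps that visible. If no patient is affected, the matching requirement changes nothing.
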